³ Please note that this rapid evidence assessment found that mentoring was more effective in reducing reoffending when contact between mentor and mentee was greater, in smaller scale studies, and when mentoring was combined with other services and interventions.

Figure 2: Sample size calculations

		Protocol	Randomisation
Minimum Detectable Effect Size (MDES)		0.19	0.186
Pre-test/ post-test correlations	Level 1 (participant)	0.0	0.5
	Level 2 (cluster)	N/A	N/A
Alpha		0.05	0.05
Power		0.8	0.8
One-sided or two-sided?		Two-sided	Two-sided
Number of participants by end of the trial	Intervention	327	337
	Control	327	349
	Total	654	686

Recruitment and baseline data collection was completed in October 2024. The cumulative T1 sample at the end of this period was 686.

337 young people were allocated to the intervention group, and 349 to the control group. This is broadly in line with the intended 1:1 allocation ratio. More information can be seen in Figure 3 below.

Referred into STEER = 1052 Eligible for STEER = Disengaged/became 997 ineligible= 316* Consented = Withdrew/excluded 694 from evaluation = 8 Baseline measures = 686 STEER= Signposting 337 = 349

Figure 3: Consort flow diagram for baseline data collection

Analysis

Overview

The following presents the analytical approach for the Efficacy Study. We currently do not know the structure of the complete data-set (for example, extent of or categories of missing data etc.) that we will receive as part of the Efficacy Study. This should be considered when interpreting the following analytical plan.

There is considerable debate about best practice when it comes to the analysis of data from RCTs. For example, Twisk et al. (2018) advocate for utilising longitudinal analysis of covariance or a repeated measures analysis without the treatment variable, but with the interaction between treatment and time in the model controlled. They argue that failure to control for baseline differences in outcomes between the groups can lead to biased estimates in the treatment. Alternatively, others have cautioned against this approach (e.g., Sen, 2013).

Based on our understanding of the literature our analysis will be conducted using General Linear Models controlling for baseline measurement of the outcome variable. An intention to treat approach will be used with all models unless otherwise stated. This in line with YEF Guidance (YEF, 2021).

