[•] These are young people who disengaged or became ineligible because they: refused the service, had a parent who refused the service, moved out of area, were uncontactable, had too many services involved, or were deemed too complex due to an escalation in risk following the acceptance of referral.

The primary outcome for the evaluation of STEER is a reduction in prevalence of self-reported offending behaviours between baseline and six months as measured by the SRDS variety score.

The secondary outcomes that we are investigating are that young people receiving STEER compared to the business as usual (control) group have (See Figure 1 for more information about measures):

- A positive relationship with their mentor.
- Improved pro-social values and behaviours.
- Improved emotional symptoms.
- Improved behaviours
- Positive relationships/role models.

The General Linear Model will include the appropriate baseline outcome measure and the treatment dummy variable. For example, for the analysis of the primary outcome measure (SRDS Variety Score) the baseline SRDS variety score measure will be included and whether the individual received STEER or not

The purpose of these analyses is to estimate the difference between the STEER arm and the business-as-usual arm for each of the primary and secondary outcomes.

Variable transformation

It is possible that the baseline and outcome variables may be skewed. Skew will be assessed using the traditional criteria based on their distribution (i.e., skews of greater or equal to 1.0 or less than or equal to -1.0). Arguably, it is more desirable to use a generalised liner model (GLM) for the appropriate modelling of non-normally distributed variables (e.g., Akram et al., 2023), than it is to transform the data.

The analytic approach has been developed a priori and will be conducted with SPSS.

The syntax for all analysis will be provided once it has been developed after all data has been collected.

Primary outcome analysis

The primary outcome is a reduction in offending measured by the SRDS Variety Score. All young people will have completed the SRDS questionnaire before randomisation and again at around six months post-randomisation.

The SRDS Variety Score is measured on a scale from 0-19 with 0 indicating the young person has not reported any of the 19 forms of delinquency/offending behaviour and a score of 19 indicating that they have undertaken all forms of delinquency/offending behaviour.

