We will be using a General Linear Model, repeated measures design (assuming normality) or a generalized linear model, repeated measures design if the SRDS Variety score is nonnormally distributed. We will include a treatment by outcome interaction term in the analysis.

This analysis is designed to evaluate the differences in SRDS Variety Score between those in STEER and those who received business as usual (i.e. the control group).

This analysis will be conducted in SPSS.

Secondary outcomes analysis

Our approach to analysis of secondary outcomes will mirror the approach outlined above for the analysis of the primary outcomes. The secondary outcomes are:

- A positive relationship between the young person and mentor measured by the Social Support and Rejection Scale (SSRS).
- Improved pro-social values and behaviours measured by the SDQ pro-social values subscale.
- Improved emotional symptoms measured by the SDQ emotional symptoms subscale.
- Improved behaviour measured by the SDQ conduct problems subscale.
- An increase in positive relationships/role models measured by the measured by the SDQ peer relationships problem subscale.

All SDQ subscales contain 5 items and are measured on scales from 0 to 10. For the prosocial values subscale high scores are desirable (e.g., greater prosocial values), but for the other subscales (e.g., emotional symptoms subscale, conduct problems subscale, peer relationship subscale) high scores are not desirable (e.g., greater emotional problems, greater conduct problems, poorer peer relationships).

The SSRS has 4 dimensions; 'Feels valued', 'Trust', 'Mentoring', and 'Negativity'. Each item is scored from 1 (never) to 5 (always). Each subscale score is the average of items that make up the subscale. Higher scores on the negativity scale reflect higher levels of stress and negativity within the relationship. For the overall scoring of the scale a high score represents a positive relationship.

We will be using general linear models, repeated measures design (assuming normality) or generalized linear models, repeated measures design if the particular subscale is non-normally distributed. This will be determined once all data has been collected. We will include a treatment by outcome interaction term in the analysis.

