We will assess missing data before analysis. We will follow YEF guidance as appropriate and report on both: (1) the number of complete cases, and (2) the extent and pattern of missingness in the data. We will also attempt to establish the missing mechanism (i.e. what variables in the data are predictive of non-response). We will explore this through logistic regression models where the presence of missing data will be modelled with additional information that may be predictive of missingness. We will conduct this analysis in line with YEF guidance and will also discuss the types of missing data in the final report as per Table 1 and using the flow chart in Figure 2 in the YEF analysis guidance. For more information see:

https://res.cloudinary.com/yef/images/v1623145483/cdn/6.-YEF-Analysis-Guidance/6.-YEF-Analysis-Guidance.pdf Extent of and reasons for missing data will be assessed and summarised in the final report.

Unfortunately, there is no universally agreed approach to analysis in the event of item non-completion. In the event that a high proportion of cases would be excluded due to low rates of item non-completion (for example, if most participants miss a small number of items), our approach to missing data will balance considerations around data integrity with maximising statistical power. In this scenario, we would consider using statistical techniques to impute missing items. We will finalise and agree our approach to this for the final draft of the Statistical Analysis Plan in line with YEF guidance, i.e. once baseline data collection is complete and we have a greater understanding of the structure of the data.

Compliance

Overall compliance for the purposes of the efficacy study will be met when young people have been randomised and allocated into the treatment or control group. This is in line with the intention to treat approach specified in the YEF Statistical Analysis Guidance (YEF, 2021).

We will explore model compliance if Power Calculations suggests the analysis will be sufficiently powered. This will explore what level of dosage was associated with a desirable outcome on the SRDS. For example, does attending 75% of STEER mandatory sessions result in a similar impact as attending all sessions? This analysis will be conducted using a general linear model, repeated measures design (assuming normality) or a generalized linear model. We will include a treatment by outcome interaction term in the analysis.

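### The SAP describes the primary model's treatment variable by receipt of STEER, which contradicts its own intention-to-treat rule; it should be stated as randomised arm

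*SAP*

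**What the plan says.** The Analysis overview sets the general principle: "An intention to treat approach will be used with all models unless otherwise stated". It then describes the model: "The General Linear Model will include the appropriate baseline outcome measure and the treatment dummy variable". The coding of that dummy is not given there. The next sentence supplies an example for the SRDS Variety Score, in which "the baseline SRDS variety score measure will be included and whether the individual received STEER or not". Straight after this, the purpose of the analyses is given as to "estimate the difference between the STEER arm and the business-as-usual arm for each of the primary and secondary outcomes".

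The section on the primary outcome says that the analysis will "evaluate the differences in SRDS Variety Score between those in STEER and those who received business as usual", and adds in brackets that the latter are the control group. The secondary analyses are to mirror the primary one. Similar receipt language appears where the overview introduces the secondary outcomes and at the end of the section on secondary outcomes.

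The Compliance section says: "Overall compliance for the purposes of the efficacy study will be met when young people have been randomised and allocated into the treatment or control" arm, and ties this to intention to treat. A separate analysis, run only if power allows, deals with the amount received: "This will explore what level of dosage was associated with a desirable outcome on the SRDS".

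Under Variable transformation, the SAP says that the syntax will be developed after all data have been collected.

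**The concern.** The example in the overview is the only place that says what the treatment variable in the primary model records, and it says receipt. Under intention to treat, the variable should record the arm assigned by randomisation. On a literal reading, a young person allocated to STEER who never engaged would be coded as untreated and pooled with the controls.

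Participation is voluntary, and the Compliance section expects attendance to vary, so some non-receipt in the STEER arm is plausible. It need not be unrelated to offending risk. If non-starters offend more than other members of their arm, coding by receipt removes poor outcomes from the STEER group and adds them to the comparison group, which favours STEER even when the programme does nothing. If they offend less, the bias runs the other way.

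Because the syntax comes after the data, the SAP text is the only advance specification of this choice. Two analysts following it could code the variable differently.

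**Working it through.** **Step 1: the passages side by side.**

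| Place in the SAP | What it points to |
|---|---|
| Analysis overview, principle | Allocation (intention to treat, exceptions only where stated) |
| Analysis overview, example for the SRDS | Receipt |
| Analysis overview, purpose (next sentence) | Allocation (arm versus arm) |
| Primary outcome analysis | Mixed: receipt wording, glossed as the control group |
| Compliance, overall definition | Allocation |
| Compliance, dosage analysis | Receipt, in a separate conditional analysis |
| Figure 2, randomisation column | Allocation (337 and 349 as allocated) |

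One sentence points clearly to receipt for the main model, and it is the one that describes the variable. The others point to allocation, but none of them codes the variable.

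**Step 2: reproduce the plan's MDES.** Inputs from Figure 2: 337 and 349 allocated (N = 686), pre/post correlation 0.5, two-sided alpha 0.05, power 0.80.

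MDES = (t₀.₉₇₅ + t₀.₈₀) × √[(1 − R²) / (P(1 − P)N)], with R² = 0.5² = 0.25, P = 337/686 and 683 degrees of freedom.

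P(1 − P)N = 337 × 349 / 686 = 171.4. The result is 0.1856, which agrees with the stated 0.186. The figure already uses the numbers as allocated, so defining the variable as randomised arm does not change it.

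**Step 3: what coding by receipt could do.** The SAP gives neither a non-start rate nor the prognosis of non-starters, so both are assumed. Let q be the share of the STEER arm that never starts and d their excess on the six-month SRDS, in SD after baseline adjustment. Take the true effect as nil, no control receiving STEER, and all 686 followed up.

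- Starters' mean: −qd. Non-starters' mean: (1 − q)d. Control mean: 0.
- By arm: (1 − q)(−qd) + q(1 − q)d = 0, so no bias.
- By receipt: bias = −qd − [337q(1 − q)d] / (349 + 337q).

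Example, q = 0.20 and d = 0.4: −0.080 − (67.4 × 0.32)/(349 + 67.4) = −0.080 − 0.052 = −0.132 SD, and 0.132/0.186 = 71% of the MDES.

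| Non-start share q | d = 0.2 SD | d = 0.4 SD |
|---|---|---|
| 5% | −0.019 (10% of MDES) | −0.038 (20%) |
| 10% | −0.036 (19%) | −0.072 (39%) |
| 20% | −0.066 (35%) | −0.132 (71%) |
| 30% | −0.091 (49%) | −0.183 (98%) |

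Negative values favour STEER. Reversing the sign of d reverses the sign of the bias.

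**The case against.** The strongest reply is that the SAP, read as a whole, already means allocation. Intention to treat applies unless an exception is stated, and an illustrative clause in an overview is hardly a stated exception. The next sentence names the two arms. The section on the primary outcome equates those who received business as usual with the control group. Compliance is defined by allocation, and dosage has its own analysis. No rule is given for how much attendance would count as having received STEER, which an as-treated variable would need.

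All of this stands as evidence of intent. A reader might infer from the example that the primary analysis will be as-treated, and the document does not support that: nowhere does it say that participants will be regrouped by what they received.

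The reply also bears on the size. Every driver of the bias is assumed. Figure 3 and its footnote put the young people who refused the service or could not be contacted among those lost before consent, so part of the self-selection came before randomisation. Non-starters who are also lost to follow-up would not enter the comparison, and the figures would change. These points stand too: the table shows what could happen, and is not an estimate for this trial.

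What the reply does not remove is the sentence itself. Evidence of intent elsewhere does not make the one description of the variable correct.

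**Conclusion.** Wrong as written. The SAP's only description of the primary treatment variable is by receipt, and this contradicts its intention-to-treat rule, its stated arm contrast and its definition of compliance. Severity is moderate: it is a contradiction in wording, and allocation is the likely intent.

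The consequence if the sentence were followed cannot be computed from the SAP. With no true effect, full follow-up, 10–30% of the STEER arm not starting and non-starters 0.2–0.4 SD worse, the bias is about 0.04–0.18 SD in favour of STEER; at 5% and 0.2 SD it is about 0.02 SD. The secondary outcomes are exposed to the same ambiguity because their analysis mirrors the primary. It would go too far to conclude that the trial's primary result will be as-treated, or that a bias of this size is expected.

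**What to change.** - In the example in the Analysis overview, replace the receipt phrase with: the arm to which the individual was randomly allocated (STEER or business as usual), whatever was received.
- Reword the introduction to the secondary outcomes in the overview, and the closing descriptions of the primary and secondary analyses, so that they refer to young people allocated to each arm.
- Use receipt of STEER only in the separate dosage analysis under Compliance.

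The change should be made before the syntax is written. It costs a few words in the SAP and one defined variable in the syntax. It needs no new data, and the MDES stays at 0.186.

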	,	Improved behaviours measured by the SDQ conduct problems sub-scale (Goodman, 2005)		
		Positive relationships/role models measured by the Peer relationships problem sub-scale in the SDQ (Goodman, 2005)		
	variable	Reduction in prevalence and variety of self-reported offending behaviours		

Baseline for primary outcome	measure (instrument, scale, source)	SRDS Variety Score
	variable	Improved pro-social values and behaviours Improved emotional symptoms Improved behaviours Positive relationships/role models
Baseline for secondary outcome	measure (instrument, scale, source)	Improved pro-social values and behaviours measured by the Strengths and Difficulties Questionnaire (SDQ) prosocial values sub-scale (Goodman, 2005) Improved emotional symptoms measured by the SDQ emotional symptoms sub-scale (Goodman, 2005) Improved behaviours measured by the SDQ conduct problems sub-scale (Goodman, 2005) Positive relationships/role models measured by the measured by the SDQ peer relationships problem subscale (Goodman, 2005)

Sample size calculations

Originally, we determined the final required participant sample size a priori, conducting Power Calculations in line with YEF guidance which suggested a total sample of 654 young people (327 per group) over the pilot trial and efficacy study would allow a statistically significant result to be identified (Power=0.80, two tailed, P<.05) for a reduction of involvement in offending of 11%. We recognised that to account for attrition STEER would need to recruit a greater number of young people to reach a final sample size of 654 by the end of the evaluation.

Our original approach was conservative and in line with Lipsey and Wilson (2001) who state that ½ d=r, which is in turn equivalent to the difference in proportions. Figure 2 shows that if we suggest that 30% of the young people that STEER does not work with commit violence compared to 20.5% of the young people that STEER does work with committing violence (equivalent to a Cohen's d=.19) a total sample of 654 (327 in each group) would be needed to detect a statistically significant result (Power=.80), in a two-tailed test (p<.05). This level of Cohen's d was selected because it is conservative and is about equivalent to a 10-11%

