difference which is in line with a weighted average effect size of mentoring programmes, based on comparisons of 18 studies in a meta-analysis of mentoring and offending using a random effects model (d=.21, 95% confidence interval .07 to .34) presented by Jolliffe and Farrington, 2008.³

Figure 2 presents the results of our power analysis at the protocol stage. It shows that in line with our conservative approach; we used a pre-test/post-test correlation of 0. This is because at the time we had no reason to believe based on data collected during the pilot trial that the variance would be different between the treatment and control group. However, we knew that inclusion of a pre-test as a covariate in impact analyses helps to explain (error) variance in the post-test and improves the likelihood of uncovering programme impacts by reducing the standard error of the impact estimate. It was difficult to estimate what the pre-test/post-test correlation would be as this depended on unknown sample characteristics and the characteristics of the measure under investigation (the SRDS when used in a sample similar to STEER, i.e., those who are known to have peers or family members involved in offending behaviour). The greater the estimated pre-test/post-test correlation the lower the MDES and the smaller the sample needed to detect this. In practice however, if the pre-test/post-test correlation changes from 0.0 to 0.4 the MDES for a sample size of 500 decreases from .25 to .23.

In line with good practice, we have conducted power analysis based on our final sample once all randomisation has been completed. This power analysis is based on the numbers involved in the trial at baseline. This is also presented in Figure 2. As part of this calculation, we have included a pre- post-test correlation of 0.5. This is based on values obtained from unpublished data from an RCT using the same outcome measure and in a similar population of adolescents (Humayun et al., 2019) which we discovered after our original power analysis for the protocol. It is also based on treating the SRDS variety score as a continuous variable in analysis as opposed to a dichotomous variable.

Our power analysis shows an MDES of 0.186 based on baseline data

SPSS 25 was used for calculations for the original protocol. PowerUp! (Dong, N. and Maynard, R. A., 2013) has been used for the calculations once all randomisation and baseline data had been completed.

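### The SAP states two unreconciled primary models, and its MDES of 0.186 fits the baseline-adjusted one but not the usual form of the repeated-measures one

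*SAP*

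**What the plan says.** The Overview of the Analysis section, after noting a debate in the literature, settles on one approach: "our analysis will be conducted using General Linear Models controlling for baseline measurement of the outcome variable". It then lists the terms as the baseline measure of the outcome and a treatment dummy, with the SRDS variety score as its worked example. That is ANCOVA.

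The Primary outcome analysis section describes something else: "We will be using a General Linear Model, repeated measures design (assuming normality) or a generalized linear model, repeated measures design", the second option applying if the score is not normally distributed. It continues: "We will include a treatment by outcome interaction term in the analysis". The repeated-measures wording recurs under Secondary outcomes analysis, Subgroup analyses, Further analyses and Compliance. The interaction sentence recurs in all of these except Further analyses.

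Under Sample size calculations the SAP reports: "Our power analysis shows an MDES of 0.186 based on baseline data". For this calculation, "we have included a pre- post-test correlation of 0.5", and the section explains the gain in precision by the pre-test acting as a covariate.

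**The concern.** In ANCOVA the baseline score is a covariate. In a repeated-measures design it is one of the two outcomes. With two waves and a treatment factor, the standard treatment-by-time test is the same as a t-test on change from baseline. It has a different variance from ANCOVA and will in general give a different p-value on the same data. Two analysts, one following the Overview and the other the Primary outcome analysis section, could therefore report different primary results and both claim to have followed the plan.

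The interaction sentence does not settle which is meant. If the term means treatment by time, it is the change-score contrast. If it means treatment by baseline score, the treatment coefficient (with baseline uncentred) is the effect for a young person with a baseline score of zero, not the average effect. The SAP never says which coefficient is the primary estimate.

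The power statement is also at stake, because the precision gained from a baseline correlation of 0.5 depends on which model is fitted.

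**Working it through.** **Inputs, all from the SAP.** Allocation: "337 young people were allocated to the intervention group, and 349 to the control group". Correlation r = 0.5. Alpha, sidedness and power: "Power=0.80, two tailed, P<.05", repeated in the Randomisation column of Figure 2. Scale: "treating the SRDS variety score as a continuous variable in analysis as opposed to a dichotomous variable", so effects are in SD units. Like the SAP, the check uses baseline numbers with no attrition.

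**Formula.** MDES = M × √f × √(1/n₁ + 1/n₂), where M is the sum of the 97.5% and 80% points of the t distribution (about 2.806 here) and f is the variance factor of the model. √(1/337 + 1/349) = 0.0764.

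**1. Reproducing the plan's figure.** With baseline as a covariate, f = 1 − r² = 0.75. MDES = 2.806 × 0.866 × 0.0764 = 0.1856, which matches 0.186. Reading 0.5 as R² instead of r would give 0.152, and ignoring baseline gives 0.214. The SAP's other illustration (500 participants, .25 falling to .23 as r goes from 0 to 0.4) also follows the covariate factor: 0.251 and 0.230. A change score at r = 0.4 would give 0.275.

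**2. Unconstrained repeated measures.** The treatment-by-time contrast has f = 2(1 − r) = 1.00, assuming equal SDs at both waves. MDES = 2.806 × 1 × 0.0764 = 0.214, the same as an analysis that ignores baseline.

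**3. Power at 0.186.** Covariate model: SE = 0.866 × 0.0764 = 0.0661, and Φ(0.186/0.0661 − 1.96) = 0.80. Change score: SE = 0.0764, and Φ(0.186/0.0764 − 1.96) = 0.68. A simulation of 10,000 trials at r = 0.5 gave 0.805 and 0.683. For 80% power at 0.186 the change-score test needs about 908 participants and the covariate model about 682; the trial has 686.

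**4. Sensitivity to r.**

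| r | MDES, covariate | MDES, change score | Power at 0.186, covariate | Power at 0.186, change score |
|---|---|---|---|---|
| 0.4 | 0.196 | 0.235 | 0.76 | 0.60 |
| 0.5 | 0.186 | 0.214 | 0.80 | 0.68 |
| 0.6 | 0.171 | 0.192 | 0.86 | 0.78 |
| 0.7 | 0.153 | 0.166 | 0.93 | 0.88 |

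**5. Constrained repeated measures.** If the treatment main effect is left out, so that baseline means are held equal, precision is essentially that of ANCOVA and the MDES is again about 0.186.

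**6. Reading the wrong coefficient.** If the treatment main effect, averaged over both waves, were taken from the unconstrained model, the MDES on the follow-up difference would be about 0.37, with simulated power of 0.29 at 0.186. This is why the plan must name the coefficient as well as the model.

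**The case against.** The strongest reply is that repeated measures as such does not invalidate 0.186. Step 5 shows that one form keeps it, and the Overview describes that form. This stands: a reader might infer that 0.186 holds only for ANCOVA, or that the trial has 68% power as planned, and the document supports neither. The loss applies to the unconstrained form. That is the ordinary meaning of a general linear model with a repeated-measures design, but the Primary outcome analysis section does not spell it out. Equally, it does not state the constraint, and the Overview presents the constrained model as one side of a debate before choosing baseline adjustment.

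It is also fair to say that the gap narrows as r rises. At r = 0.7 even the change-score test does better than 0.186.

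Three further inferences would go too far:

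- **Hedges' g.** It is computed under Presentation of outcomes from arm means and variances, so it remains available whichever model is fitted. It would simply not correspond to the coefficient of a model on another scale.
- **The generalized-model switch.** It is not wholly open, because Variable transformation gives a skew criterion of ±1.0. The distribution and link are not stated, so a switch may change the scale of the effect rather than certainly doing so.
- **Bias from dropout.** Change scores can be more exposed than ANCOVA to dropout that depends on baseline and differs by arm. The SAP gives no follow-up dropout data, however, and linear ANCOVA is itself unbiased only if the baseline relation is right.

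**Conclusion.** The contradiction is real and concerns the primary test of an efficacy trial. The Overview and the power calculation agree on baseline as a covariate; the Primary outcome analysis section does not, and its interaction term is undefined. Under the usual unconstrained reading, the MDES rises from 0.186 to 0.214 and power at 0.186 falls from about 80% to about 68%. Those figures rest on r = 0.5, equal SDs at both waves, a continuous outcome and no attrition. They are what one reading of the text would cost, not a finding that the trial is underpowered. The need to name one model and one coefficient does not depend on them.

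**What to change.** In the Primary outcome analysis section, state one model that matches the Overview and the power calculation: six-month SRDS variety score on randomised arm plus baseline SRDS variety score, with the coefficient for arm as the primary estimate. Delete the repeated-measures wording and the interaction sentence there.

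Align the Secondary outcomes, Further analyses and Compliance sections. For the SSRS, Figure 1 lists no baseline measure although the Introduction has all measures collected at both waves, so say whether a baseline value is available as a covariate. Under Subgroup analyses, replace the term with a treatment-by-subgroup interaction, since an interaction is needed there.

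If repeated measures is kept instead, define the interaction as treatment by time and say whether baseline means are constrained equal. If they are not, restate the MDES as 0.214.

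If the skew rule leads to a generalized model, keep baseline as a covariate and note that 0.186 does not directly describe that model's effect.

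The cost is SAP wording only, with no new data or change to trial conduct.
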